3.7.4.5.2. CCI [Redacted text]

[Redacted text block]

[Redacted text block]

3.7.4.5.3. CCI [Redacted text]

[Redacted text block]

Protocol 331-12-283

CCI [Redacted text block]

3.7.4.5.4. CCI [Redacted text block]

Protocol 331-12-283

3.7.4.5.5. Mini-Mental State Examination (MMSE)

The MMSE⁴³ is a brief practical test for assessing cognitive dysfunction. The test consists of 5 sections (orientation, registration, attention and calculation, recall, and language) and has a total possible score of 30. The MMSE is used for screening subjects (refer to [Table 3.4.3-1](#)) and is also to be completed at Week 12/ET. A sample of the MMSE is provided in [Appendix 20](#).

3.7.5. Pharmacokinetic Assessments

3.7.5.1. Blood Collection Times

Pharmacokinetic samples will be collected at baseline and at any time during Week 8 and Week 12/ET. If blood samples for clinical laboratory tests are not collected at the baseline visit, pharmacokinetic samples do not need to be obtained at baseline. The samples will be collected at the same time as clinical laboratory sample collection for the designated trial visits, if applicable. Every possible effort should be made to collect pharmacokinetic samples at the same time at each visit. Furthermore, the subject should be advised to take the IMP at approximately the same time each day throughout the trial, but most importantly, prior to each pharmacokinetic sampling. The date and time of the last 2 doses of IMP prior to each sample draw, and the date and time of the actual blood draw will be recorded on the eCRF.

3.7.5.2. Sample Handling and Processing

Details for drawing and processing pharmacokinetic samples are provided in [Appendix 21](#).

3.7.6.

CCI [Redacted]

[Redacted]

Protocol 331-12-283

CCI [Redacted text block]

3.7.6.1. CCI [Redacted]

[Redacted text block]

3.7.6.2. CCI [Redacted]

[Redacted text block]

Protocol 331-12-283

CCI [Redacted]

3.7.7. End of Trial

The end-of-trial date is defined as the last date of contact or the date of final contact attempt from the post-treatment follow-up eCRF page for the last subject completing or withdrawing from the trial.

3.7.8. Independent Data Monitoring Committee

The DMC will monitor safety in subjects who participate in the trial. The DMC meetings will occur as outlined in the DMC Charter, but can be convened at any time at the discretion of the DMC chair or the trial medical officer. The chair will be notified by the trial medical officer of all SAEs and will receive summaries of other safety data as available.

The responsibilities of the DMC include:

- Evaluating the progress of the trial, subjects’ risk versus benefit, and other factors that could affect the trial outcome
- Considering relevant information that may have an impact on the safety of the participants or the ethics of the trial

3.7.9. CCI [Redacted]

[Redacted]

Protocol 331-12-283

3.8. Stopping Rules, Withdrawal Criteria, and Procedures

3.8.1. Entire Trial or Treatment Arm(s)

If the sponsor terminates or suspends the trial for safety or unanticipated other reasons, prompt notification will be given to investigators, IRBs/IECs, and regulatory authorities in accordance with regulatory requirements.

3.8.2. Individual Site

A particular center may be terminated from the trial at the discretion of the investigator, sponsor, or IRB/IEC, eg, for non-enrollment of subjects or noncompliance with the protocol. The investigator will notify the sponsor promptly if the trial is terminated by the investigator or the IRB/IEC at the site.

3.8.3. Individual Subject

If a subject discontinues the trial prematurely, the reason must be fully evaluated and recorded appropriately in source documents and the eCRF. If the subject is being withdrawn because of an AE, the AE should be indicated as the reason for withdrawal.

All subjects have the right to withdraw at any time during treatment without prejudice. The investigator can discontinue a subject's participation in the trial at any time if medically necessary. In addition, subjects meeting any of the following criteria must be withdrawn from the trial:

- 1) Occurrence of any AE, intercurrent illness, or abnormality in a laboratory assessment that, in the opinion of the investigator, warrants the subject's permanent withdrawal from the trial
- 2) Treatment with a prohibited concomitant medication other than the use of appropriate medications for the treatment of AEs under direction of the investigator
- 3) Subject noncompliance, defined as refusal or inability to adhere to the trial schedule or procedures (see [Section 3.12, Subject Compliance](#))
- 4) At the request of the subject, caregiver, legally acceptable representative, investigator, sponsor, or regulatory authority
- 5) Subject becomes pregnant
- 6) Subject cannot tolerate the assigned dose of brexpiprazole (or matching placebo)
- 7) Subject develops clinically significant agitation per investigator's judgment that cannot be adequately treated with allowed medications and poses a potential safety risk to the subject and/or others
- 8) Subject is lost to follow-up

Protocol 331-12-283

- 9) Subject transfers from an institutionalized setting to a non-institutionalized setting, or vice versa. In case of a brief hospitalization, determination of subject eligibility to stay in the trial must be made based on subject safety by the investigator and medical monitor.

CCI

The investigator will notify the sponsor promptly when a subject is withdrawn. Subjects withdrawn prior to Week 12 must complete the Week 12/ET evaluations at the time of withdrawal. In addition, all subjects who withdraw prematurely from the trial will be assessed 30 (+2) days after the last dose of the IMP for evaluation of safety. This assessment can be accomplished at a clinic visit at either the investigator's site or residential facility, if applicable. If a clinic visit is not possible, the subject should be assessed by telephone contact with the subject and a caregiver. CCI

Three attempts will be made to contact the subject's caregiver by telephone; in the event the site is unable to reach the subject's caregiver by telephone, the site will attempt to contact the subject's caregiver via certified mail or an alternative similar method where appropriate.

Any subject who withdraws prematurely from the trial will not be eligible to roll-over into Trial 331-13-211.

Meeting a screening exclusion criterion postrandomization does not require an automatic discontinuation of the subject. The investigator should assess the change for clinical significance, determine if an AE should be reported, and make a determination of subject continuation based on subject safety. The investigator could consult with the medical monitor to determine subject continuation in the trial.

Protocol 331-12-283

3.9. Screen Failures

A screen failure is a subject from whom a signed ICF is obtained, but who has not started on treatment. For this trial, treatment begins with the first dose of the IMP. If a subject fails to qualify for the trial during the 42-day screening period for a reason other than a positive screen for cocaine, marijuana, or other illicit drugs, the subject is permitted to be rescreened at a later date. A subject may be rescreened more than once after discussion with and approval by the medical monitor. The medical monitor must be contacted before rescreening any subjects who initially failed screening due to a positive blood alcohol test or positive drug screens resulting from use of prescription or OTC medications or products. In the event that the subject is rescreened for trial participation, a new ICF must be signed, a new screening number assigned, and all screening procedures repeated.

3.10. Definition of Completed Subjects

The treatment period is defined as the time period during which subjects are evaluated for primary or secondary objectives of the trial irrespective of whether or not the subject was administered all doses of the IMP. Subjects who are evaluated at the last scheduled visit during the treatment period will be defined as trial completers. For purposes of this trial, subjects who complete the Week 12 visit will be defined as trial completers.

3.11. Definition of Subjects Lost to Follow-up

Subjects who cannot be contacted on or before the Week 12 visit during the treatment period and who do not have a known reason for discontinuation (eg, withdrew consent or AE) will be classified as “lost to follow-up.” If an institutionalized subject leaves the residential facility in which he/she was residing before completion of the trial, the site will make 3 attempts to contact the subject by telephone; in the event the site is unable to reach the subject by telephone, the site will attempt to contact the subject via certified mail or an alternative similar method where appropriate. A similar procedure will be followed for non-institutionalized subjects who are lost to follow-up.

3.12. Subject Compliance

Responsible trial personnel will dispense the IMP (ie, brexpiprazole or matching placebo) according to the visits outlined in the Schedule of Assessments ([Table 3.7-1](#)). Accountability and compliance verification should be documented in the subject’s trial records.

Protocol 331-12-283

For non-institutionalized subjects, the caretaker or caregiver may administer IMP to the subject, as long as the subject is compliant with IMP dosing requirements.

For institutionalized subjects, the caregiver will be responsible for administering IMP to the subject. It may be possible that there is more than one caregiver for a subject. The caregiver(s) should be appropriately instructed to ensure that the subject is compliant with IMP dosing requirements.

3.13. Protocol Deviations

In the event of a significant deviation from the protocol due to an emergency, accident, or mistake (eg, violation of informed consent process, IMP dispensing or subject dosing error, treatment assignment error, subject enrolled in violation of eligibility criteria or concomitant medication criteria), the investigator or designee will contact the sponsor's designee (medical monitor) at the earliest possible time by telephone. The investigator and sponsor's designee (medical monitor) will come as quickly as possible to a joint decision regarding the subject's continuation in the trial. This decision will be documented by the investigator and the sponsor and reviewed by the site monitor.

4. Restrictions

4.1. Prohibited Medications

All subjects must discontinue all prohibited medications during the screening period to meet the protocol-specified washout periods. The required duration of washout for selected prohibited medications is provided in [Table 4.1-1](#). All other psychotropic agents not listed in [Table 4.1-1](#) are prohibited and must be discontinued at least 24 hours before the first dose of IMP. The oral benzodiazepine therapy permitted during the trial is summarized in [Table 4.1-3](#).

Protocol 331-12-283

Table 4.1-1 List of Restricted and Prohibited Medications			
All other psychotropic agents not listed in the below table are prohibited and must be discontinued at least 24 hours before the first dose of IMP.			
	Medication	Prior to Randomization	During Double-Blind Treatment Period
1.	Medications to treat Alzheimer's disease (cholinesterase inhibitors, memantine, and/or other cognitive enhancers)	Allowed provided that the dose has been stable for 90 days prior to randomization	Subject should remain on the same dose throughout the duration of the trial, except when medically indicated due to a change in the underlying medical condition.
2.	Antipsychotics	7-day washout	Prohibited
	Clozapine	Not allowed within 30 days prior to randomization.	Prohibited
	Depot or long-acting injectable antipsychotic drugs	Washout of 1.5 times the dosing interval (according to the prescribing information)	Prohibited
3.	Antidepressants	Allowed provided that the dose has been stable for 30 days prior to randomization. Antidepressant medications that are CYP2D6 or CYP3A4 inhibitors are prohibited and require a 7-day washout; fluoxetine requires a 28-day washout (see Table 4.1-2 for prohibited antidepressant medications).	Subject should remain on the same dose throughout the duration of the trial, except when medically indicated due to a change in the underlying medical condition. Antidepressant medications that are CYP2D6 or CYP3A4 inhibitors are prohibited.
4.	Mood stabilizers (such as lithium, valproate, carbamazepine)	7-day washout	Prohibited
5.	Anticonvulsants	7-day washout	Prohibited
6.	Benzodiazepines (short-acting) ^{a,b}	Allowed but limited to 4 days/week with a maximum dose of 2 mg/day of lorazepam (or equivalent) or less depending on dose-limiting side effects.	During the first 4 weeks of the randomized phase (baseline to Week 4 visit): allowed but limited to 4 days/week with a maximum dose of 2 mg/day of lorazepam (or equivalent) or less depending on dose-limiting side effects. Benzodiazepines must not be administered within 12 hours prior to the efficacy and safety scales. After Week 4 visit: Prohibited

Protocol 331-12-283

Table 4.1-1 List of Restricted and Prohibited Medications			
All other psychotropic agents not listed in the below table are prohibited and must be discontinued at least 24 hours before the first dose of IMP.			
	Medication	Prior to Randomization	During Double-Blind Treatment Period
7.	Non-benzodiazepine sleep agents ^c	If a bedtime dose of a sleep agent for insomnia was taken prior to screening on a regular basis, a stable pretrial dose of the sleep agent may be continued as needed during the trial. If a sleep agent was not previously taken prior to screening and needs to be initiated, medication should be limited to a maximum dose of 5 mg/day of zolpidem (or equivalent).	Sleep agents must not be administered within 8 hours prior to the efficacy and safety scales. Combined use of benzodiazepines and non-benzodiazepine sleep agents for insomnia is not allowed.
8.	Opioid analgesics	Prohibited unless permission is obtained from the medical monitor. Permission for opioid use may be considered for a documented and clinically appropriate indication (eg, episodic pain condition, tooth extraction) if prescribed at a medically appropriate dose and frequency.	Prohibited unless permission is obtained from the medical monitor. Permission for opioid use may be considered for a documented and clinically appropriate indication (eg, episodic pain condition, tooth extraction) if prescribed at a medically appropriate dose and frequency.
9.	Anticholinergics for treatment of extrapyramidal symptoms ^d	7-day washout	Prohibited
10.	Propranolol ^e	For treatment of akathisia or tremor: 7-day washout For treatment of heart disease: allowed provided that the dose has been stable for 30 days prior to randomization and total dose does not exceed 60 mg/day	For treatment of akathisia or tremor: maximum dose of 20 mg, 3 times daily (total of 60 mg/day). For treatment of heart disease: may remain on stable pretrial doses as needed throughout the trial, as long as the total dose does not exceed 60 mg/day. Propranolol must not be administered within 12 hours prior to the efficacy and safety scales.
11.	Varenicline	7-day washout	Prohibited
12.	Medications to treat other medical conditions, such as hypertension, hypercholesterolemia, etc., and anti-platelet agents	Allowed provided that the dose has been stable for 30 days prior to randomization	Subject should remain on the same dose throughout the duration of the trial, except when medically indicated due to a change in the underlying medical condition.

Protocol 331-12-283

Table 4.1-1 List of Restricted and Prohibited Medications			
All other psychotropic agents not listed in the below table are prohibited and must be discontinued at least 24 hours before the first dose of IMP.			
	Medication	Prior to Randomization	During Double-Blind Treatment Period
13.	Nutritional supplements and nonprescription herbal preparations with CNS effects (eg, St. John's wort, omega-3 fatty acids, kava extracts, gamma-aminobutyric acid (GABA) supplements, etc)	7-day washout	Prohibited
14.	Cytochrome P450 2D6 isozyme (CYP2D6) inhibitors or CYP3A4 inhibitors and inducers (see Table 4.1-2)	7-day washout	Prohibited

^aUse of intramuscular benzodiazepines are prohibited throughout the trial. However, limited use of specific oral benzodiazepines is permitted during screening and during the first 4 weeks of the randomization phase (baseline to Week 4 visit) to treat agitation and/or insomnia (see [Table 4.1-3](#)).

^bBenzodiazepines must not be administered within 12 hours prior to scheduled efficacy and safety scales, including EPS scales. Investigators are encouraged to delay scale administration until 12 hours have elapsed, if at all possible. However, if delaying administration of efficacy and safety scales is not feasible, the scales should still be administered and the use of benzodiazepine documented, including a notation of the drug name, dose, and time of administration on the eCRF.

^cNon-benzodiazepine sleep aids (ie, zolpidem, zaleplon, zopiclone, and eszopiclone only) are permitted for the treatment of insomnia, but not on the same day as administration of a benzodiazepine, regardless of indication. For the non-benzodiazepine sleep aids, sites should only utilize one of the listed medications that are approved for this indication in their respective countries and the country-specific prescribing information is to be used to determine the maximum allowable daily dose for the treatment of insomnia. Non-benzodiazepine sleep aids must not be administered within 8 hours prior to scheduled efficacy and safety scales, including EPS scales. Investigators are encouraged to delay scale administration until 8 hours have elapsed, if at all possible. However, if delaying administration of efficacy and safety scales is not feasible, the scales should still be administered and the use of the sleep aid documented, including a notation of the drug name, dose, and time of administration on the eCRF.

^dAnticholinergic treatment of extrapyramidal symptoms (eg, benztropine) is not permitted within the 7 days prior to randomization and for the duration of the trial.

^ePropranolol must not be administered within 12 hours prior to scheduled efficacy and safety scales, including EPS scales. Investigators are encouraged to delay scale administration until 12 hours have elapsed, if at all possible. However, if delaying administration of efficacy and safety scales is not feasible, the scales should still be administered and the use of propranolol documented, including a notation of the drug name, dose, and time of administration on the eCRF.

Protocol 331-12-283

Table 4.1-2 Selected CYP2D6 Inhibitors and CYP3A4 Inhibitors and Inducers	
Type	Examples (Generic Names)
CYP2D6 Inhibitors	Celecoxib, chloroquine, chlorpheniramine, clemastine, clomipramine, diphenhydramine, duloxetine, fluoxetine ^a , halofantrine, hydroxyzine, methadone, moclobemide, paroxetine, pyrilamine, quinidine, terbinafine, tripeleonnamine
CYP3A4 Inhibitors	Amiodarone, amprenavir, aprepitant, chloramphenicol, cimetidine, clarithromycin, clotrimazole (if used orally), delavirdine, diltiazem, erythromycin, fluconazole, fluvoxamine, indinavir, itraconazole, ketoconazole, nefazodone, nelfinavir, quinupristin/dalfopristin, ritonavir, saquinavir, troleandomycin, verapamil
CYP3A4 Inducers	Carbamazepine, dexamethasone, efavirenz, nevirapine, oxcarbazepine, phenobarbital, phenytoin, primidone, rifampin, St. John's wort, troglitazone

^aFluoxetine requires a 28-day washout prior to randomization.

Table 4.1-3 Oral Benzodiazepine Therapy During the Trial		
Oral Benzodiazepine^{a,b}	Maximum Allowable Daily Dose (mg/day)	
	Screening (limited to 4 days/week)	Baseline to Week 4 Visit (limited to 4 days/week)
Lorazepam	2	2
Oxazepam	30	30

^aBenzodiazepines must not be administered within 12 hours prior to scheduled efficacy and safety scales, including EPS scales. Investigators are encouraged to delay scale administration until 12 hours have elapsed, if at all possible. However, if delaying administration of efficacy and safety scales is not feasible, the scales should still be administered and the use of benzodiazepine documented, including a notation of the drug name, dose, and time of administration on the eCRF.

^bIn countries where no short-acting benzodiazepines are commercially available, use of oral diazepam (maximum allowable daily dose of 10 mg/day) or oral clonazepam (maximum allowable daily dose of 1 mg/day) may be acceptable if prior authorization is obtained from the medical monitor.

4.2. Other Restrictions

The following restrictions apply:

- Subjects should not undergo any elective medical procedure without prior consultation with the investigator. An elective procedure (minor surgery, dental surgery, orthopedic surgery, etc.) that might require hospitalization or general anesthesia should be deferred until after the trial whenever clinically appropriate.
- Consumption of grapefruit, grapefruit products, Seville oranges, or Seville orange products within 72 hours prior to the first dose of IMP and during the trial is prohibited.
- Subjects should refrain from drinking alcoholic beverages or using illicit drugs during participation in the trial.

Protocol 331-12-283

- The investigator may request a blood or urine drug screen at any time during the trial if there is a suspicion of illicit drug use.
- Treatment with other investigational agents is not permitted during the trial.

New onset nonpharmacological interventions for the treatment of agitation are not permitted during the double-blind treatment period. Subjects who have been treated with nonpharmacological interventions prior to trial entry may continue these therapies during the double-blind treatment period.

5. Reporting of Adverse Events

5.1. Definitions

An AE is defined as any untoward medical occurrence associated with the use of a drug in humans, whether or not considered drug related.

A suspected adverse reaction means any AE for which there is a reasonable possibility that the drug caused the AE. For the purpose of IND safety reporting, “reasonable possibility” means there is evidence to suggest a causal relationship between the drug and the AE. Suspected adverse reaction implies a lesser degree of certainty about causality.

An SAE includes any event that results in any of the following outcomes:

- 1) Death
- 2) Life-threatening, ie, the subject was, in the opinion of the investigator, at immediate risk of death from the event as it occurred. It does not include an event that, had it occurred in a more severe form, might have caused death.
- 3) Persistent or significant incapacity or substantial disruption of the ability to conduct normal life functions.
- 4) Requires in-patient hospitalization or prolongs hospitalization (NOTE: A prescheduled hospitalization is not considered an SAE.)
- 5) Congenital anomaly/birth defect
- 6) Other medically significant events that, based upon appropriate medical judgment, may jeopardize the subject and may require medical or surgical intervention to prevent one of the outcomes listed above, eg, allergic bronchospasm requiring intensive treatment in an emergency room or home, blood dyscrasias or convulsions that do not result in hospitalization, or the development of drug dependency or drug abuse.

Non-serious adverse events are AEs that do not meet the criteria for an SAE.

Protocol 331-12-283

If a subject is experiencing an extrapyramidal symptom, the specific extrapyramidal symptom must be indicated on the AE page of the eCRF. Examples of AEs that are considered extrapyramidal symptoms include, but are not limited to: generalized rigidity, dyskinesia, hyperkinesia, bradykinesia, akinesia, dystonia, hypertonia, akathisia, tremor, flexed posture, involuntary muscle contractions, athetosis, and chorea. If a subject is experiencing two or more of these symptoms, whether or not treatment with an anticholinergic is required, this is considered as extrapyramidal syndrome and must be entered as “extrapyramidal syndrome” on the AE page of the eCRF instead of the individual symptoms.

Immediately Reportable Event (IRE)

- Any SAE
- Any AE that necessitates discontinuation of the IMP
- Potential Hy’s law cases (any increase of AST or ALT ≥ 3 times the ULN with an increase in total bilirubin ≥ 2 times the ULN)

Pregnancies are also defined as IREs. Although normal pregnancy is not an AE, it will mandate IMP discontinuation and must be reported on an IRE form to INC Research. Pregnancy will only be documented on the AE eCRF if there is an abnormality or complication.

Clinical Laboratory Changes

It is the investigator’s responsibility to review the results of all laboratory tests as they become available. This review will be documented by the investigator’s dated signature on the laboratory report. For each abnormal laboratory test result, the investigator needs to ascertain if this is an abnormal (ie, clinically significant) change from baseline for that individual subject. (This determination, however, does not necessarily need to be made the first time an abnormal value is observed. The investigator may repeat the laboratory test or request additional tests to verify the results of the original laboratory tests). If this laboratory value is determined by the investigator to be an abnormal change from baseline for that subject, this is considered an AE.

Protocol 331-12-283

Severity

All AEs will be graded on a 3-point scale and reported as indicated on the eCRF. The intensity of an adverse experience is defined as follows:

- 1 = Mild: Discomfort noticed, but no disruption to daily activity
- 2 = Moderate: Discomfort sufficient to reduce or affect normal daily activity
- 3 = Severe: Inability to work or perform normal daily activity

IMP Causality

The causal relationship of an AE to the use of the IMP will be assessed as follows:

- Related: There is a reasonable possibility of a causal relationship
- Possibly related: There is a reasonable causal relationship between the IMP and the AE. Dechallenge is lacking or unclear
- Unlikely related: There is a temporal relationship to the IMP administration, but there is not a reasonable causal relationship between the IMP and the AE
- Not related: There is no temporal or reasonable relationship to the IMP administration

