In Trial 331-09-222, randomized subjects received a flexible dose of brexpiprazole 1 to 3 mg/day (average dose 2.2 mg/day) or placebo as adjunctive treatment to an assigned open-label ADT. In this trial, the MADRS Total Score decreased at each visit for both brexpiprazole and placebo groups, however, the decrease observed in the brexpiprazole group was statistically significant from baseline at all visits except the primary endpoint visit. The MADRS response rate ($\geq 50\%$ decrease MADRS Total Score) and remission rate (MADRS Total Score ≤ 10) were statistically significant at endpoint. Brexpiprazole at doses up to 3 mg/day was well tolerated when administered as adjunctive therapy to a marketed ADT in subjects with MDD. During the double-blind treatment phase, TEAEs were reported in 76.2% of subjects in the brexpiprazole group and 63.6% of subjects in

Protocol 331-12-283

the placebo group. The most frequently reported TEAEs were akathisia (11.9%), increased weight (11.4%), and insomnia (9.2%). The Columbia-Suicide Severity Rating Scale (C-SSRS) and adverse event (AE) data showed no suicidal behavior during double-blind treatment. No serious adverse events (SAEs) were reported for subjects in the brexpiprazole group, and 3 subjects (1.6%) in the placebo group experienced an SAE; 4.9% of subjects who received adjunctive brexpiprazole and 1.1% of subjects who received adjunctive placebo discontinued treatment due to TEAEs. There were no clinically relevant changes in laboratory values, ECG parameters, or vital sign measurements, except body weight (mean increase of 1.92 kg in the brexpiprazole group versus 0.13 kg in the placebo group), in brexpiprazole-treated subjects. The minimal changes in scores for EPS scales during double-blind treatment were not clinically relevant. An EPS-related AE was observed in 21.6% of subjects in the brexpiprazole group compared with 9.6% of subjects in the placebo group.

Trial 331-08-212 is an ongoing, 52-week, open-label trial examining the long-term safety and tolerability of brexpiprazole in adults with MDD. Subjects who complete trials 331-08-211 or 331-09-222 are eligible to enter this trial.

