Subjects must have been residing at their current location for at least 14 days before screening and be expected to remain at the same location for the duration of the trial. Subjects who at any point during the double-blind treatment phase transfer from an institutionalized setting to a non-institutionalized setting, or vice versa, will be withdrawn from the trial. In case of a brief hospitalization, determination of subject eligibility to stay in the trial must be made based on subject safety by the investigator and medical monitor. All attempts should be made to maintain the subjects’ normal routine with regard to appointments with physicians and overnight accommodations. Subjects in an institutionalized setting may receive supervised day passes at the discretion of the investigator and may also receive supervised overnight passes at the discretion of the investigator as long as such overnight stays are part of the subjects’ normal routine.

CCI

It is planned that approximately 840 subjects will be screened at approximately 85 trial sites worldwide in order to randomize approximately 420 subjects.

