7.6.1. Adverse Events

All AEs will be coded by system organ class and Medical Dictionary for Regulatory Activities (MedDRA) preferred term. The incidence of the following events will be summarized by treatment group:

- 1) TEAEs by severity
- 2) TEAEs potentially causally related to the IMP

Protocol 331-12-283

- 3) TEAEs with an outcome of death
- 4) Serious TEAEs
- 5) Discontinuations due to TEAEs

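### Section 5.1 replaces co-occurring extrapyramidal symptoms with one syndrome entry, so the recorded incidence of akathisia, tremor, dyskinesia and similar single terms is too low

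*Protocol*

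**What the plan says.** Section 5.1 of the protocol (Definitions) sets two recording rules for extrapyramidal symptoms.

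- **One symptom:** "the specific extrapyramidal symptom must be indicated on the AE page of the eCRF". The examples given include "dyskinesia, hyperkinesia, bradykinesia, akinesia, dystonia, hypertonia, akathisia, tremor", and the list is stated not to be exhaustive.
- **Two or more:** "If a subject is experiencing two or more of these symptoms, whether or not treatment with an anticholinergic is required", the event counts as *extrapyramidal syndrome* and must be entered under that name "on the AE page of the eCRF instead of the individual symptoms".

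The second rule is mandatory and takes no account of severity. The AE section asks for no companion field that lists the component symptoms.

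On analysis, Section 7.6.1 states: "All AEs will be coded by system organ class and Medical Dictionary for Regulatory Activities (MedDRA) preferred term". It then calls for incidence by treatment group, including by severity and by potential causal relation to the IMP. Section 3.5.6 likewise has AEs examined by frequency, severity, seriousness, discontinuation and relationship to treatment.

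Outside the AE page, Section 4.1 refers to "scheduled efficacy and safety scales, including EPS scales". The descriptions of these scales are redacted in the public copy. Section 9.2 requires progress notes that record the severity, frequency, duration, action taken and outcome of any AE.

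**The concern.** The two rules give the same symptom different fates according to what accompanies it. Akathisia alone is counted as akathisia. Akathisia with tremor is counted as neither. A table row for akathisia then shows the subjects who had akathisia and no other extrapyramidal symptom, although a reader will take it as the subjects who had akathisia.

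The loss happens at data capture. An analysis plan can group preferred terms, but it cannot split one syndrome entry into its parts, or give each part its own onset, severity or causality. For that reason this is a matter for the protocol and the eCRF guideline and cannot be left to the SAP.

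Safety and tolerability of the two fixed doses against placebo is the secondary objective (Section 2.3). These symptoms are known for this drug. Section 1.2.2.1 reports akathisia as the most frequent TEAE in Trial 331-09-222, and Section 1.3 lists it among the frequent TEAEs in both the schizophrenia and the depression trials.

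**Working it through.** The protocol states no expected rate of extrapyramidal events and no share of subjects with two or more symptoms, so there is no figure of its own to reproduce. The check is to follow a subject from the eCRF to the table, then illustrate the size.

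**Step 1: trace the entry.** How a subject adds to the preferred-term counts:

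| Subject has | Akathisia | Tremor | Extrapyramidal syndrome | Any extrapyramidal AE |
|---|---|---|---|---|
| Akathisia only | 1 | 0 | 0 | 1 |
| Tremor only | 0 | 1 | 0 | 1 |
| Akathisia and tremor, rule as written | 0 | 0 | 1 | 1 |
| Akathisia and tremor, each entered | 1 | 1 | derived | 1 |

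The single-term counts can only fall. The last column is unchanged, provided the grouping includes the syndrome term.

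**Step 2: formula.** Let *p* be the true incidence of a symptom and *m* the share of subjects with that symptom who also have another listed one.

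Recorded incidence = *p* × (1 − *m*)

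**Step 3: inputs, for illustration only.**
- *p* = 11.9%, the akathisia rate reported for Trial 331-09-222 (Section 1.2.2.1).
- About 420 subjects randomized 1:1:1 (Section 3.3), so 420 / 3 = 140 per arm.
- *m* = 10%, 25% or 40%. These are assumptions; the protocol gives no value.

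**Step 4: result.** With each symptom entered, 140 × 0.119 = 16.7 subjects would be counted under akathisia.

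| *m* (assumed) | Recorded incidence | Recorded subjects of 140 |
|---|---|---|
| 10% | 11.9 × 0.90 = 10.7% | 15.0 |
| 25% | 11.9 × 0.75 = 8.9% | 12.5 |
| 40% | 11.9 × 0.60 = 7.1% | 10.0 |

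**Step 5: difference between arms.** With subscripts *a* for active and *c* for placebo:

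Recorded difference = (*p_a* − *p_c*) − (*p_a m_a* − *p_c m_c*)

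Take 11.9% on active against an assumed 3% on placebo, a true difference of 8.9 points.
- *m* = 10% in both arms: 11.9 × 0.90 − 3 × 0.90 = 8.0 points.
- *m* = 30% against 10%: 11.9 × 0.70 − 3 × 0.90 = 5.6 points.

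The answer depends entirely on *m* in each arm and on the placebo rate, none of which the protocol supplies.

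**The case against.** Four points can fairly be made on the other side.

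1. **No subject disappears.** Affected subjects move to a visible syndrome row in the same tables, and the count of subjects with any extrapyramidal AE stays intact if that term is grouped with the others. Section 1.2.2.1 itself reports Trial 331-09-222 by such a grouped measure (21.6% against 9.6%), and Section 7.6 leaves the details of the safety analysis to the SAP. This stands. A reader might infer that the rule flattens the dose-response or the drug-placebo contrast for extrapyramidal effects as a whole. The protocol does not support that: the grouped contrast survives, and the effect on single terms by arm is unknown. Section 1.3 does report more extrapyramidal symptoms at the highest dose in Trial 331-07-203, but that dose was 5 ± 1 mg/day in schizophrenia, and the text says nothing about co-occurrence.

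2. **A later symptom need not displace an earlier one.** A reader might infer that a second symptom weeks later overwrites the first. The present tense of the rule reads most naturally as concurrent symptoms, and nothing tells sites to delete an entry. What stands is an ambiguity: the text does not state concurrency, nor what happens to a symptom already entered, so sites may differ.

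3. **Other records exist.** Rating scales and progress notes may hold the component information. This stands as partial mitigation, but neither is stated to feed the preferred-term tables.

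4. **The percentages are not a forecast.** The 11.9% comes from a flexible-dose adjunctive trial in depression. If that trial used the same recording rule, its rate is already net of the loss. The shares are assumed. This stands in full.

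Nor does the rule single out the most severely affected. It turns on the number of symptoms, so one severe symptom alone is still recorded under its own name.

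**Conclusion.** The point holds for individual preferred terms. Followed as written, Section 5.1 under-records the incidence of akathisia, tremor, dyskinesia and each other listed symptom whenever it occurs with another, and it removes their separate severity and onset from the AE page. The direction is certain; the loss is zero only if no subject has two symptoms.

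The size and any imbalance between arms cannot be derived from the protocol. The fall from 11.9% to between 10.7% and 7.1% rests on a borrowed rate and assumed shares of 10% to 40%. The primary and key secondary efficacy analyses are not touched, and neither is the incidence of any extrapyramidal AE if the syndrome term is grouped in. This is a modest weakness in safety data capture that is cheap to correct and worth correcting, because it cannot be repaired from the AE page afterwards.

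**What to change.** Amend Section 5.1 and the eCRF completion guideline as follows.

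- Enter every extrapyramidal symptom as its own AE, with onset, severity and outcome.
- Define the syndrome as two or more concurrent symptoms, and derive it programmatically from the dates or capture it with an added check-box.
- Report the syndrome beside the individual terms.

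This keeps the sponsor's category, settles the concurrency question and removes any doubt about symptoms already entered. It changes no treatment or follow-up.

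The cost is a short change to one section and its guideline, and a few more AE lines per affected subject. The synopsis carries the date 10 Sep 2015, and Appendix 22 dates the protocol that Amendment 1 changed to 18 Feb 2013, so enrolment may already have begun. If so, earlier syndrome entries should be queried for their components, so that the AE dataset follows one convention throughout.
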